15. STATISTICS

The data obtained in the study will be analyzed using SPSS 25.0. Descriptive statistical methods such as number, percentage, mean, and standard deviation will be used in the data analysis. Based on the results, the data will be analyzed using relevant tests (t-test, chi-square, Man-Whitney U, Fisher's exact, and regression analysis).

H0: Prehabilitation does not affect patient outcomes in fragile cases undergoing elective coronary artery bypass grafting.

H1: Prehabilitation affects patient outcomes in fragile cases undergoing elective coronary artery bypass grafting.

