1. SUMMARY

Title of the Study : Investigation of the Effect of Prehabilitation on Patient Outcomes in Frail Patients Planned for Elective Coronary Artery Bypass Graft

Rationale : To see the effect of preoperative routine and improved practices on the patient after surgery.

Purpose : The purpose of the research is, To determine the effect of prehabilitation care on patient outcomes.

Objective : To evaluate the effect of preoperative prehabilitation on patient outcomes and contribute to the literature.

Population : Frail patients scheduled for elective coronary artery bypass grafting at the University of Health Sciences, Istanbul Mehmet Akif Ersoy Thoracic and Cardiovascular Surgery Training and Research Hospital.

Number of Volunteers : The sample calculation of the study was made using Power (G-power) analysis, and the minimum sample size was calculated as 30 patients for both groups, while the Type I error amount was 0.05 and the power of the test was 0.80 ($\alpha=0.05$, $1-\beta=0.80$).

Research Design : The study was planned as a randomized controlled trial.

Procedure : After obtaining institutional approval, the study will continue until the sample size is reached with patients who meet the criteria. Patients identified with the preoperative mini mental test and frailty scale will be administered a patient information form, mini nutritional test, Charlson Comorbidity Index, and Duke activity status index 3-4 weeks before surgery in the intervention group, and 1 day before surgery in the control group. Before postoperative discharge, the appropriate section of the patient information form and the Clavien Dindo classification will be administered and recorded. On the 30th

postoperative day, the mini nutritional test, Duke activity status index, activities of daily living scale, and postoperative recovery index will be administered and recorded.

Research Duration : After obtaining institutional permission, the study will continue until the sample size is reached on patients who meet the criteria.

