5. PURPOSES

The aim of the study is to determine the effect of prehabilitation care on patient outcomes.

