8. POPULATION TO BE STUDIED

How was the sample size decided: It was decided by G-power analysis.

Number of volunteers planned to be included: 30+30

Volunteer Age Range: 60+

- Agreeing to participate in the research,
- Undergoing elective open coronary artery bypass grafting
- Being 60 years old or older,
- Being in the frail patient status as a result of the FRIED Frailty Scale,
- Being able to communicate in Turkish.

Exclusion Criteria: Patients whose surgery has been postponed and those whose mini mental test result is 23 or below will not be included.

Gender: Male and female

Are there any vulnerable groups/individuals (children, disabled people, unconscious individuals) planned to be included?

Yes No

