13. EVALUATION AND PARAMETERS TO BE RECORDED

Patients will be interviewed face-to-face and a "Patient Information Form," prepared by the researchers based on literature, will be completed. A mini mental test and frailty scale will be used to select patients. A preoperative mini nutritional test, comorbidity scale, 6-minute walk test, and Borg scale will be used for both groups. A patient information form and complication classification will be completed before discharge. On the 30th postoperative day, a mini nutritional test, activities of daily living scale, postoperative recovery index, 6-minute walk test, and Borg scale will be used.

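### No visible passage names a primary outcome: the single hypothesis covers patient outcomes collectively, and the stated alpha, power and sample size are tied to none of them

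*Protocol*

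**What the plan says.** Section 5 gives the objective: "The aim of the study is to determine the effect of prehabilitation care on patient outcomes". Section 15 sets one null and one alternative, the latter reading "H1: Prehabilitation affects patient outcomes in fragile cases undergoing elective coronary artery bypass grafting". Neither has a direction, a named scale or a time point.

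The measures that could count as outcomes are listed in several places. Section 13 has a complication classification before discharge, and then: "On the 30th postoperative day, a mini nutritional test, activities of daily living scale, postoperative recovery index, 6-minute walk test, and Borg scale will be" applied. The Summary's postoperative list includes the Duke index but neither the 6-minute walk nor the Borg scale. Sections 9 and 13 include those two and leave the Duke index out.

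The error rates appear once, in the Summary: "while the Type I error amount was 0.05 and the power of the test was 0.80". Section 8 gives the size, "Number of volunteers planned to be included: 30+30", and its basis, "It was decided by G-power analysis". No outcome, test, effect size or standard deviation accompanies them. Section 15 offers a menu of tests and makes the choice among them depend on results, which may mean no more than distributional checks. It gives no ordering of outcomes and no multiplicity adjustment.

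**The concern.** A confirmatory hypothesis has to say which result would confirm or refute it, and this one does not. Taken literally, the null is that prehabilitation changes none of the outcomes, so a difference on any single scale contradicts it, in either direction and whatever the other scales show. With several scales each tested at 0.05, the chance of at least one false positive exceeds 0.05. The headline scale could also be picked after the data are seen. The trial could then conclude that prehabilitation affects patient outcomes on the strength of one scale among several, with no defined error rate behind that conclusion.

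The power statement has the same gap. A reader cannot tell for which measure, and for what difference, 30 per group gives 0.80.

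**Working it through.** **Inputs from the protocol.** Alpha 0.05 and power 0.80 (Summary); 30 per group (Section 8); the outcome lists below. Sidedness, effect size and correlations between outcomes are not given.

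**Counting the outcomes.**

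| Place | Postoperative measures | Count |
|---|---|---|
| Summary | Clavien-Dindo, nutrition, Duke, daily living, recovery index | 5 |
| Sections 9 and 12 | nutrition, daily living, recovery index, 6-minute walk, Borg | 5 |
| Section 13 | the five of Section 9 plus complication class | 6 |
| Union of all lists | the six of Section 13 plus Duke | 7 |

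No single section schedules seven. Items within the patient information form are not counted.

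**The plan's own figure.** The 30 per group cannot be reproduced without an effect size, so it is solved backwards. For a two-sample t-test with 30 per group, alpha 0.05 and power 0.80, the standardised difference is d = 0.736 two-sided (0.650 one-sided). Check with the normal approximation at d = 0.74: n = 2 × (1.960 + 0.842)² / 0.74² = 15.70 / 0.5476 = 28.7, so 29 per group; the exact t calculation gives 30. At d = 0.5 the two-sided power with 30 per group would be 0.48.

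**False-positive rate if any significant outcome counts.** For k independent outcomes, each tested at two-sided 0.05, the rate is 1 − 0.95^k:

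- k = 5: 1 − 0.774 = 0.226
- k = 6: 1 − 0.735 = 0.265
- k = 7: 1 − 0.698 = 0.302

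Positive correlation lowers this. The table shows a simulation of two-sided t-tests with 30 per arm, no true effect on any outcome, an equal pairwise correlation r (an assumption) and 40,000 trials per setting:

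| r | k = 6 | k = 7 |
|---|---|---|
| 0.3 | 0.240 | 0.271 |
| 0.5 | 0.209 | 0.230 |
| 0.7 | 0.165 | 0.182 |
| 0.9 | 0.109 | 0.116 |

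Against 0.05, the range runs from 0.109 / 0.05 = 2.2 times to 0.302 / 0.05 = 6.0 times.

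**If all outcomes stayed confirmatory under Bonferroni.** Alpha per test would be 0.05/6 = 0.0083 or 0.05/7 = 0.0071. At d = 0.736 on an outcome, power at 30 per group falls from 0.80 to 0.55 (six outcomes) or 0.53 (seven). About 47 or 48 per group would be needed to restore 0.80.

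**The case against.** The strongest reply is that Section 15 never says that any significant result confirms H1. It states a global hypothesis and a list of tests, and is silent on how several results become one decision. A multiplicity rule is commonly left to the statistical analysis plan, and one may exist. That is correct. A reader might infer that the protocol adopts an any-outcome rule and that 0.05 is certainly exceeded, but the document supports neither. The percentages above are conditional on that rule.

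A reader might also infer that an alpha and power pair can only describe one test of one outcome. This is not shown: the calculation has no stated basis, and Section 15 lists regression among the tests, so an omnibus calculation cannot be excluded.

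The size of the inflation is also open to challenge. Seven is a union of lists that disagree, and no correlation is documented. If Fisher's exact test were used for complications, its conservatism would lower the figures somewhat. Finally, some pages were removed before review, including the text between Sections 13 and 15, so the statement can only be about what is visible.

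What survives is narrower but firm. The protocol itself fixes a hypothesis, an alpha, a power and a sample size. Saying which outcome they serve belongs with them and is not analysis detail. A later Bonferroni rule would protect the 0.05 but, as shown, at a cost in power for each outcome that the sample-size statement does not mention.

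**Conclusion.** The point holds in a limited form. No visible section designates a primary outcome, the hypothesis and aim are collective, the outcome lists conflict, and alpha, power and 30+30 are linked to no outcome or effect size. Nothing visible protects the stated 0.05.

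If each outcome is tested at two-sided 0.05 and any significant result counts, the false-positive rate is 23% to 30% for five to seven independent outcomes. For six or seven outcomes it is about 21% to 23% at an assumed correlation of 0.5, 16% to 18% at 0.7 and 11% to 12% at 0.9. A claim of at least a threefold excess would require ruling out high correlation, which the protocol does not allow; roughly two to six times is the supportable range. Every case examined exceeds 0.05, but the exact size depends on assumptions.

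**What to change.** 1. Reconcile the outcome lists in the Summary and Sections 9, 12 and 13, so that the family of outcomes is fixed.
2. In Sections 5 and 15, name one already collected outcome and its time point as primary, and restate H0 and H1 on it. The choice is the sponsor's, preferably the measure used in the G-power calculation. Walk distance on postoperative day 30 is one example: it is listed in Sections 9, 12 and 13 and fits the functional-capacity rationale in Section 4, although the Summary's procedure omits it.
3. Make and record the choice without sight of outcome data by group. Section 3 dates data collection from 28 May 2025 and analysis from 1 April 2026, so data may already have accrued.
4. Label the remaining measures secondary and state that they do not decide H1.
5. State the effect size behind 30+30 for the primary outcome. If the calculation used another measure, do not simply carry the 0.80 across. Restate the power for the chosen outcome, or give the detectable difference at 30+30: about 0.74 standard deviations for 80% power at two-sided 0.05.

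The cost is a protocol amendment, with no new measurements or visits if the outcome is already collected. The price is that a positive result on a secondary scale alone can no longer confirm H1. The stated power may also prove less favourable, and if 0.74 is implausible for the chosen outcome, the sample size itself comes into question.

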16. SUB-STUDY

No.

17. INFORMED VOLUNTARY CONSENT

Before the surgery, the patient will be visited in the room, informed and consent will be obtained before data collection.

18. RESEARCH BUDGET

Budget

Coverage of research expenses & Sponsor declaration

(The costs of tests and laboratory examinations performed on volunteers for research purposes cannot be covered by public or private health insurance, nor can they be paid by the volunteers. The costs of all research-related procedures, such as printing survey/interview forms, fees for services such as consultancy, tests, and laboratory examinations received from within or outside the institution, reimbursement of volunteer expenses, telephone charges to reach volunteers, payments to researchers/interviewers, etc., must be planned and their source must be explained.)

There are no anticipated expenses.

Research Funds (TÜBİTAK etc. Please write the name:

Other (Please Explain):

Research expense items (Adjust the possible expense items below according to your research. You can add or remove items if necessary. If there are no projected expenses, leave them blank.)	AMOUNT
 Payments to researchers	
 Payments to be made to the research institution	
 Payments to be made to volunteers	
 Service purchases from the research site	
 Service purchases outside the research site	
 Consumable purchases	
 Stationery purchases	
 Travel expenses	

